11.5 Analysis of secondary variables

The secondary efficacy variables include,

- response to treatment at Week 16 according to the ASAS40 criteria
- change from baseline in hsCRP at Week 16
- response to treatment at Week 16 according to the ASAS5/6 criteria
- change from baseline in total BASDAI score at Week 16
- change in SF-36 PCS from baseline at Week 16
- change in ASQoL from baseline at Week 16
- response to treatment at Week 16 according to the ASAS partial remission

All analysis will be done in the FAS population.

Testing strategy to control type I error

The following null hypotheses will be included in the testing strategy, and type-I-error will be set such that a family-wise type-I-error of 5% is kept:

Primary objectives:

H₁: secukinumab 150 mg regimen is not different to placebo regimen with respect to signs and symptoms (ASAS20 response) at Week 16

Secondary objectives:

H₂: secukinumab 150 mg regimen is not different to placebo regimen with respect to signs and symptoms (ASAS40 response) at Week 16

H₃: secukinumab 150 mg regimen is not different to placebo regimen with respect to change from baseline in hsCRP at Week 16

H₄: secukinumab 150 mg regimen is not different to placebo regimen with respect to ASAS 5/6 response at Week 16

[figure not shown]
H₅: secukinumab 150 mg regimen is not different to placebo regimen with respect to change from baseline in total BASDAI at Week 16

H₆: secukinumab 150 mg regimen is not different to placebo regimen with respect to change from baseline in SF-36 PCS at Week 16

H₇: secukinumab 150 mg regimen is not different to placebo regimen with respect to change from baseline in ASQoL at Week 16

H₈: secukinumab 150 mg regimen is not different to placebo regimen with respect to ASAS partial remission criteria at Week 16

Figure 11-1 Testing strategy

The family-wise error will be set to $\alpha=5\%$ and it will be controlled with the proposed closed testing procedure.

The secondary efficacy variables and the method for adjusting for multiplicity are described below. Secondary efficacy variables will be analyzed using the FAS population.

ASAS40 at Week 16

The ASAS 40 response is defined as an improvement of $\geq 40\%$ and ≥ 2 units on a scale of 10 in at least three of the four main domains and no worsening at all in the remaining domain.

Response at Week 16 to ASAS40 in the FAS will be evaluated using a logistic regression model with treatment, randomization stratum (region) as factors and baseline weight as a covariate. Odds ratios and 95% CI will be presented for comparison performed between secukinumab and placebo at Week 16.

hsCRP at Week 16

For the hsCRP, since evidence from the literature would suggest that the data is not normally distributed ([Huffman 2006](#)), analysis will be performed on the \log_e ratio of the treatment value vs. baseline value (calculated by dividing the post-baseline value by the baseline value and then applying the \log_e transformation) to normalize the distribution of hsCRP at each analysis visit. Between-treatment differences in the hsCRP relative to baseline will be evaluated using a mixed-effect model repeated measures (MMRM) with treatment group, analysis visit, and randomization stratum (region) as factors and \log_e baseline hsCRP and baseline weight as continuous covariates. Treatment by analysis visit and \log_e baseline hsCRP by analysis visit will be included as interaction terms in the model. An unstructured covariance structure will be assumed for the model. The significance of the secukinumab treatment effect will be determined from comparison performed between secukinumab regimen and placebo at Week 16. The estimate and the 2-sided 95% confidence intervals obtained from the model will be back transformed to the original scale.

ASAS 5/6 at Week 16

The ASAS 5/6 improvement criteria is an improvement of $\geq 20\%$ in at least five domains.

The proportion of subjects meeting the response criteria at Week 16 will be evaluated using a logistic regression model with treatment group, randomization stratum (region) as factors and baseline weight as a covariate. Odds ratios and 95% CI will be presented for comparison performed between secukinumab regimen and placebo at Week 16.

BASDAI at Week 16

Between-treatment differences in the change from baseline in BASDAI will be evaluated using a mixed-effect model repeated measures (MMRM) with treatment group, analysis visit, and randomization stratum (region) as factors, baseline BASDAI score and baseline weight as continuous covariates. Treatment by analysis visit and baseline BASDAI score by analysis visit will be included as interaction terms in the model. An unstructured covariance structure will be assumed for the model. The significance of the secukinumab treatment effect at Week 16 will be determined from comparison performed between secukinumab regimen and placebo at Week 16.

SF-36 PCS and ASQoL at Week 16

[figure not shown]
See [Section 11.7](#).

[figure not shown]
ASAS partial remission at Week 16

Response at Week 16 to ASAS partial remission criteria will be evaluated using a logistic regression model with treatment, randomization stratum (region) as factors and baseline weight as a covariate. Odds ratios and 95% CI will be presented for comparison performed between secukinumab regimen and placebo at Week 16.

Sensitivity analysis for hierarchy variables using patient's global assessment of disease activity (VAS)

During the data cleaning review process prior to database lock, a patient was found to have had a baseline value for “patient’s global assessment of disease activity (VAS)” completed out of sequence during a post-baseline visit, as documented in the vendor’s audit trail. Since this variable is a component of ASAS20, ASAS40 and ASAS 5/6 that require the calculation of change from baseline, a sensitivity analysis using the same logistic regression analysis for these hierarchy variables excluding this baseline value will be done.

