4.1 Inclusion criteria

Patients eligible for inclusion in this study have to fulfill **all** of the following criteria:

1. Patient must be able to understand and communicate with the investigator and comply with the requirements of the study and must give written, signed and dated informed consent before any study assessment is performed
2. Male or non-pregnant, non-lactating female patients at least 18 years of age
3. Diagnosis of moderate to severe AS with prior documented radiologic evidence (x-ray or radiologist's report) fulfilling the Modified New York criteria for AS ([Appendix 3](#)),
4. Active AS assessed by BASDAI ≥ 4 (0-10) **at Baseline**
5. Spinal pain as measured by BASDAI question #2 ≥ 4 cm (0-10 cm) **at Baseline**
6. Total back pain as measured by VAS ≥ 40 mm (0-100 mm) **at Baseline**
7. Patients should have had inadequate response or failure to respond to at least 2 NSAIDs at an approved dose for a minimum of 4 weeks in total and a minimum of 2 weeks for each NSAID prior to randomization, or less than 4 weeks if therapy had to be withdrawn due to intolerance, toxicity or contraindications
8. Patients who are regularly taking NSAIDs (including COX-1 or COX-2 inhibitors) as part of their AS therapy are required to be on a stable dose for at least 2 weeks before randomisation
9. Patients who have been on a TNF α inhibitor (not more than one) must have experienced an inadequate response to previous or current treatment given at an approved dose for at least 3 months prior to randomization or have been intolerant to at least one administration of an anti-TNF α agent
10. Patients who have previously been on a TNF α inhibitor will be allowed to entry into study after an appropriate wash-out period prior to randomization:
 - a. 4 weeks for Enbrel $^{\circledR}$ or "Yi Sai Pu" $^{\circledR}$ (etanercept) – with a terminal half-life of 102 \pm 30 hours (s.c. route)
 - b. 8 weeks for Remicade $^{\circledR}$ (infliximab) – with a terminal half-life of 8.0-9.5 days (s.c. route)
 - c. 10 weeks for Humira $^{\circledR}$ (adalimumab) – with a terminal half-life of 10-20 days (average 2 weeks) (s.c. route)
 - d. 10 weeks for Simponi $^{\circledR}$ (golimumab) – with a terminal half-life of 11-14 days
 - e. 10 weeks for Cimzia $^{\circledR}$ (certolizumab) – with a terminal half-life of 14 days

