6.4.1.4 ASAS partial remission criteria

The ASAS partial remission is defined as a value not above 2 units in each of the four main domains on a scale of 10.

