9.5.1.5 ASAS partial remission

Response at Week 16 to ASAS partial remission criteria will be evaluated using a logistic regression model with treatment, randomization stratum (region) as factors and weight as a covariate.

9.5.1.6 Change from baseline of SF-36 PCS and ASQoL at Week 16

See [Section 9.5.4](#) Health-related Quality of Life.

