9.5.1.7 Testing strategy

The following hypotheses will be tested each at 5% level of significance in pre-specified order as mentioned below using fixed-sequence test such that a family-wise type-I-error of 5% is kept:

Primary objectives:

H1: secukinumab 150 mg regimen is not different to placebo regimen with respect to signs and symptoms (ASAS20 response) at Week 16

Secondary objectives:

H2: secukinumab 150 mg regimen is not different to placebo regimen with respect to signs and symptoms (ASAS40 response) at Week 16

H3: secukinumab 150 mg regimen is not different to placebo regimen with respect to change from baseline in hsCRP at Week 16

H4: secukinumab 150 mg regimen is not different to placebo regimen with respect to ASAS 5/6 response at Week 16

[figure not shown]
H5: secukinumab 150 mg regimen is not different to placebo regimen with respect to change from baseline in total BASDAI at Week 16

H6: secukinumab 150 mg regimen is not different to placebo regimen with respect to change from baseline in SF-36 PCS at Week 16

[figure not shown]
H7: secukinumab 150 mg regimen is not different to placebo regimen with respect to change from baseline in ASQoL at Week 16

H8: secukinumab 150 mg regimen is not different to placebo regimen with respect to ASAS partial remission criteria at Week 16

Figure 9-1 Testing Strategy

The family-wise error will be set to $\alpha=5\%$ and it will be controlled with the proposed closed testing procedure.

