11.7 Analysis of health-related quality of life variables

Ankylosing Spondylitis Quality of Life (ASQoL)

For the change in ASQoL scores, between-treatment differences in the change in ASQoL scores will be evaluated using a mixed effect repeated measures model (MMRM). Treatment group, analysis visit, randomization stratum (region) will be used as categorical factors and baseline ASQoL score and baseline weight as continuous covariates. Treatment by analysis visit and baseline ASQoL score by analysis visit will be included as interaction terms in the model. An unstructured covariance structure will be assumed for the model. The significance of the secukinumab treatment effect at different analysis visits will be determined from comparison performed between secukinumab regimen and placebo at the appropriate analysis visits.

The proportion of subjects with improvements from baseline in ASQoL score meeting or exceeding minimal clinically important difference (MCID) will also be analyzed using a logistic regression model with treatment and randomization stratum (region) as factors, baseline ASQoL score and baseline weight as covariates up to Week 16. Odds ratios and 95% CI will be presented for treatment comparison. Post Week 16 the proportion of responders will be descriptively summarized along with its 95% confidence intervals for each treatment sequence.

SF-36

The following variables will be evaluated:

[figure not shown]
- SF-36 domain scores (based on a scale of 0-100).
- SF-36 PCS and MCS scores (norm-based scores).
- SF-36 PCS responder (improvement of ≥ 2.5 points, [Lubeck 2004](#))

For the change in SF-36 summary scores (PCS and MCS), between-treatment differences will be evaluated using a mixed effect repeated measures model (MMRM). Treatment group, analysis visit and randomization stratum (region) will be included as categorical factors and baseline SF-36 score (PCS or MCS) and baseline weight as continuous covariates. Treatment by analysis visit and baseline SF-36 score (PCS or MCS) by analysis visit will be included as interaction terms in the model. An unstructured covariance structure will be assumed for the model. The significance of the secukinumab treatment effect at different analysis visits will be determined from comparison performed between secukinumab regimen and placebo at the appropriate analysis visits.

[figure not shown]

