In the responder analyses, treatment groups will be compared with respect to response to treatment using a logistic regression model with treatment and randomization stratum (region)

[figure not shown]
as factors, baseline SF-36 PCS score and baseline weight as covariates up to Week 16. Odds ratios and 95% CI will be presented for treatment comparison. Post Week 16, the proportion of responders will be descriptively summarized along with its 95% confidence intervals for each treatment sequence.

The SF-36 domain scores will be summarized.

12 [REDACTED] evaluations (change / add PD, [REDACTED]/PD,
Biomarkers, as needed)

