16.2.2.2 Logistic regression

Certain binary outcome variables, e.g. response outcomes, will be evaluated using a logistic regression model. The model will include factors and covariates as specified for respective analysis. The SAS code below outlines a template for the analysis where covariates can be added or removed as required:

```
ods output diff=lsm_diff convergencestatus=conv_status;
proc logistic data=;
by visit;
class treatment strata / param=glm;
model response = treatment strata weight;
lsmeans treatment / diff cl exp;
run;
```

In cases where separation is a concern, e.g. 0% or 100% response for some treatment and covariate level combination, an exact logistic regression model may be applied to all visits. To help with convergence, this model will not include any continuous covariates. The SAS code below outlines a template for the analysis where covariates can be added or removed as required:

```
ods output exactoddsratio=exact_or;
proc logistic data=data exactonly;
by visit;
class treatment strata / param=ref;
model response = treatment strata;
exact treatment / estimate=odds;
run;
```

When exact logistic regression is unable to be implemented (due to computational complexity as the procedure can lead to extremely long run times), then Fisher's exact test will be applied. In this case, only a p-value for a test of equal response in the two groups can be obtained (no odds ratios or confidence intervals can be estimated.)

```
ods output fishersexact=fisher;
proc freq data=;
by visit;
table treatment*response / fisher;
run;
```

Input dataset should only contain data from the two treatment groups to be compared.

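### Optional: the ASAS partial remission (H8) model adjusts for no baseline disease score; adding baseline BASFI could gain 0 to about 2 points of power, depending on an assumed prognostic strength

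*SAP*

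**What the plan says.** Protocol 9.5.1.5 and SAP 11.5 give the same H8 model. The protocol has "ASAS partial remission criteria will be evaluated using a logistic regression model with treatment, randomization stratum (region) as factors and weight as a covariate"; the SAP, which specifies baseline weight, has "ASAS partial remission criteria will be evaluated using a logistic regression model with treatment, randomization stratum (region) as factors and baseline weight as a covariate". The endpoint itself is "defined as a value not above 2 units in each of the four main domains on a scale of 10" (protocol 6.4.1.4), so it is a level reached, not a change from baseline.

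Protocol 9.5.1.7 has the hypotheses "tested each at 5% level of significance in pre-specified order as mentioned below using fixed-sequence test", with H8 last. SAP Table 15-1 gives H8 the lowest power, 92% for 13.9% against 4.1%; every other endpoint is given 99%.

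Elsewhere the SAP does use a baseline score: in its MMRMs, and in the responder models of SAP 11.7, which have "baseline ASQoL score and baseline weight as covariates up to Week 16" for ASQoL and "as factors, baseline SF-36 PCS score and baseline weight as covariates up to Week 16" for SF-36 PCS. Models with other baseline characteristics are mentioned only as optional supportive work on ASAS20 (protocol 9.4.4).

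If separation is a concern, SAP 16.2.2.2 allows exact logistic regression: "To help with convergence, this model will not include any continuous covariates".

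**The concern.** A patient who enters with poor function has further to travel to reach 2 units or less in all four domains than one who enters near that level. If a baseline score predicts remission, leaving it out of a logistic model pulls the treatment log odds ratio towards zero and costs some power. H8 has the least power to spare. Because it is last in the sequence, its model can change without touching any other test. What is at stake is a small part of the roughly 7% chance of missing H8 when the planning rates hold, not the validity of the analysis.

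**Working it through.** **Inputs.** Two-sided 5%; 300 against 150 patients; 13.9% against 4.1% (SAP 15 and 15.1); about 80% from China (protocol 3.1). Expected responders are 300 × 0.139 = 41.7 and 150 × 0.041 = 6.15. The effect of a baseline score on remission is not in the documents and is varied below.

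**The plan's own figure.** Full enumeration of Fisher's exact test gives 91.9% with each tail at 0.025, or 93.1% with the minimum-likelihood two-sided rule. The stated 92% is reproduced.

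**Reaching H8.** Under the planning tables, the chances of failing the earlier tests are: ASAS20 0.000001, ASAS40 0.000010, BASDAI 0.000005, SF-36 PCS 0.000010 and ASQoL 0.000039, with hsCRP and ASAS 5/6 negligible. They sum to about 0.000065, below 0.01%. H8's own power is therefore in effect its overall power.

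**Gain from one score.** Trials were simulated with 80% China in each arm, weight and region without effect, and a standard normal score with coefficient β on the log odds. Intercepts were solved so that the marginal rates stay at 13.9% and 4.1%. Each trial was analysed with treatment, region and weight, then with the score added. The two Wald columns come from separate sets of trials.

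| β per SD | Wald, 20,000 trials | Wald, 40,000 trials | Likelihood ratio, 40,000 trials |
|---|---|---|---|
| 0 | -0.06 | -0.05 | 0.0 |
| 0.3 | +0.1 | +0.2 | +0.1 |
| 0.5 | +0.5 | +0.6 | +0.4 |
| 0.7 | +1.1 | +1.0 | +0.7 |
| 1.0 | +1.9 | +1.8 | +1.4 |

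Entries are changes in power, in percentage points, from a planned-model Wald power of about 93%. At β = 0.5 two further sets gave +0.55 (30,000 trials) and +0.3 (20,000). The mean weighted by trials (in thousands) is (40 × 0.6 + 30 × 0.55 + 20 × 0.5 + 20 × 0.3)/110 = 0.51, so +0.5 is a fair summary.

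The range has no fixed ceiling. An odds ratio of 3 per SD (β = 1.10) gave +2.2 and an odds ratio of 4 gave +3.1. If both planning rates are cut by 10% for dropout counted as non-response, odds ratios of 1.5, 2 and 3 gave +0.3, +1.1 and +2.5.

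**Validity.** With a common rate of (41.7 + 6.15)/450 = 10.6%, Wald rejection was 4.67% without and 4.66% with the score at β = 0.3, and 4.65% and 4.85% at β = 1.0 (difference 0.20 ± 0.23).

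**Precision.** The median standard error of the log odds ratio rises from 0.450 to 0.452, 0.455 and 0.468 at β = 0.3, 0.5 and 1.0. The gain comes from a larger conditional log odds ratio, not from a narrower interval.

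**Missing baseline scores.** With 2% missing and filled by the overall mean, gains were +0.2, +0.3 and +2.0 at β = 0.3, 0.5 and 1.0, against +0.2, +0.3 and +1.9 with complete scores in the same trials.

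**Exact fallback.** The non-China placebo cell has about 150 × 0.20 = 30 patients. The chance of no responder there is 0.959^30 = 0.285, or about 29% in simulation. If the fallback were used whenever this happened, the gain would be about +0.5 at β = 0.5 and +1.7 at β = 1.0. A smaller check of 10,000 trials gave a fall from 0.5 to 0.4 and from 1.6 to 1.4.

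**The case against.** The strongest reply is that nothing is wrong. H8 is adequately powered, no other test depends on it, and the benefit rests on a prognostic strength that the documents do not supply. For a weak to moderate score it is half a point or less. That stands, and it is why the point is optional.

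Three costs also stand. All four ASAS binary endpoints in the sequence now share one covariate set, and H8 would leave it. The odds ratio becomes conditional on BASFI. The score drops out if the exact fallback is used, although that rule is discretionary.

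Timing matters too. SAP 11.5 already refers to a finding from data cleaning before database lock, so the text was written late, and the documents reviewed do not settle whether unblinding has followed.

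A reader might infer that the SAP is inconsistent because its ASQoL and SF-36 PCS responder models carry a baseline score. The documents do not support that. Those models score improvement on their own instrument and lie outside the testing sequence. They are a precedent for a baseline term, not evidence of an omission.

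**Conclusion.** The point holds as an optional improvement. The H8 model contains no baseline disease score, and one named score would raise Wald power from about 93.0% by about 0 to 2 points for log odds ratios per SD from 0 to 1.0, by less on the likelihood-ratio test, and by more than 2 points only for a stronger score. If the score is useless, no loss is detectable.

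These figures assume the planning rates, no effect of region or weight, and a single roughly normal score. They do not show that BASFI is prognostic in this population.

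The gain is an average over chance imbalances. At β = 0.5, when the active arm starts more than 0.1 SD sicker (15.7% of trials), power goes from 90.2% to 94.2%; when it starts more than 0.1 SD healthier (15.6%), it goes from 95.0% to 92.7%.

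It would be wrong to read this as showing that H8 is underpowered, that its type I error is affected, or that the other ASAS models need the same change. Those other endpoints are already given 99% power.

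**What to change.** Only if the study is still blinded:

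- Add baseline BASFI as one further covariate to the H8 logistic model in SAP 11.5.
- Fill a missing baseline score with the overall mean, so that no FAS patient is dropped.
- Document the deviation from protocol 9.5.1.5.

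BASFI is a sensible choice. It is one of the four domains, is collected at baseline (Table 6-1), and has no entry minimum, whereas protocol 4.1 truncates BASDAI, spinal pain and total back pain at 4 of 10. It also avoids the out-of-sequence baseline global assessment described in SAP 11.5.

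Leave the ASAS20, ASAS40 and ASAS 5/6 models and the exact-logistic rule as they are. If Week 16 unblinding has occurred, leave H8 as planned.

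The cost is a short SAP edit and one documented deviation, with no new data. In return the sponsor accepts a more conditional odds ratio with a slightly larger standard error, and a covariate set that differs from the other ASAS endpoints.

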11.7 Analysis of health-related quality of life variables

Ankylosing Spondylitis Quality of Life (ASQoL)

For the change in ASQoL scores, between-treatment differences in the change in ASQoL scores will be evaluated using a mixed effect repeated measures model (MMRM). Treatment group, analysis visit, randomization stratum (region) will be used as categorical factors and baseline ASQoL score and baseline weight as continuous covariates. Treatment by analysis visit and baseline ASQoL score by analysis visit will be included as interaction terms in the model. An unstructured covariance structure will be assumed for the model. The significance of the secukinumab treatment effect at different analysis visits will be determined from comparison performed between secukinumab regimen and placebo at the appropriate analysis visits.

The proportion of subjects with improvements from baseline in ASQoL score meeting or exceeding minimal clinically important difference (MCID) will also be analyzed using a logistic regression model with treatment and randomization stratum (region) as factors, baseline ASQoL score and baseline weight as covariates up to Week 16. Odds ratios and 95% CI will be presented for treatment comparison. Post Week 16 the proportion of responders will be descriptively summarized along with its 95% confidence intervals for each treatment sequence.

SF-36

The following variables will be evaluated:

[figure not shown]
- SF-36 domain scores (based on a scale of 0-100).
- SF-36 PCS and MCS scores (norm-based scores).
- SF-36 PCS responder (improvement of ≥ 2.5 points, [Lubeck 2004](#))

For the change in SF-36 summary scores (PCS and MCS), between-treatment differences will be evaluated using a mixed effect repeated measures model (MMRM). Treatment group, analysis visit and randomization stratum (region) will be included as categorical factors and baseline SF-36 score (PCS or MCS) and baseline weight as continuous covariates. Treatment by analysis visit and baseline SF-36 score (PCS or MCS) by analysis visit will be included as interaction terms in the model. An unstructured covariance structure will be assumed for the model. The significance of the secukinumab treatment effect at different analysis visits will be determined from comparison performed between secukinumab regimen and placebo at the appropriate analysis visits.

[figure not shown]
In the responder analyses, treatment groups will be compared with respect to response to treatment using a logistic regression model with treatment and randomization stratum (region)

[figure not shown]
as factors, baseline SF-36 PCS score and baseline weight as covariates up to Week 16. Odds ratios and 95% CI will be presented for treatment comparison. Post Week 16, the proportion of responders will be descriptively summarized along with its 95% confidence intervals for each treatment sequence.

The SF-36 domain scores will be summarized.

12 [REDACTED] evaluations (change / add PD, [REDACTED]/PD,
Biomarkers, as needed)

